Title: The Outcome of Sports Vision Training on Collegiate
Softball Players

NCT number: Not assigned.

Protocol ID: 2022-1225-EXP

Date: 04 Aug 2023

Research statistical analysis plan.

This is a within-subject before-after design to assess the efficacy of sports vision training on functional visual skills. Parametric repeated measures ANOVA will be used with post-hoc t-tests corrected for multiple comparisons. After completion 2 main outcomes will be evaluated: 1) a Senaptec Sensory re-evaluation will be performed to compare visual skill performance to the baseline evaluation. Results are compared to other Division 1 softball athletes in Senaptec's database and percentiles are given for each individual athlete for each skill evaluated. 2) a comparison of baseline training performance to post training performance in sports vision training activities, such as Dynavision and Senaptec Sensory Trainer activities. To analyze change in training performance, a student's T-test will be utilized to measure effect size and look for statistical significance. Analysis will utilize both individual and team comparisons. We will evaluate the impact of the sports vision program by comparing baseline values to final values for each primary outcome measure. A recommendation from literature review that we will heed, is suggesting we need to adjust the significance level, to account for multiple tests being performed, the multiple comparison correction so that statistics are not artificially inflated to significance when they are truly not.

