Title: The Outcome of Sports Vision Training on Collegiate
Softball Players

NCT number: Not assigned.

Protocol ID: 2022-1225-EXP

Date: 04 Aug 2023

Protocol for Softball Study:

Goals to address in vision training: increase eye hand coordination, peripheral awareness, visualization, concentration, depth perception, anticipation, contrast sensitivity, target accuracy, and decrease reaction time.

There are 23 ladies on the softball team. There is an eight week vision training protocol developed, not including the pre-evaluation and post evaluations, wash out and final evaluation. The training will be a required once per week 45 minute training session. They will have signups for 2 per hour so we can ensure high quality training, with strict adherence to the protocol.

There are eight tasks for each session. It was recommended to change the order of the task each week to account for order effects. So I have different training sheets for each week stapled to their others for continuity. The week one training sheets are in the Softball Folder. Please be diligent in keeping track of time, as to not go over time. You must follow the specific order of activities each week. If a conflict arises, then please make a note on which activities were completed out of order.

I have timed the protocol to be 38 minutes when I walked through it so that leaves a few minutes for changing areas etc.

No one is allowed to engage with the study participants unless they have given me their CITI training, this includes the Optometry students. If in doubt do not engage with the participants.

Most of the activity's difficulty can be adjusted to be MORE difficult for progression. They cannot be made easier than the base protocol though, so please do NOT make any activity easier. If you run out of time to complete a task just note it.

General Coaching Guidelines:

1. Always use positive reinforcement. Patients should always be verbally rewarded for good effort. If a patient is unsuccessful at the required task, the therapist should encourage the patient and commend his hard work.
2. Always ask patient how their eyes feel and how they are doing throughout each task. The therapist should try to establish an awareness on the part of the patient of what they are doing to keep the targets clear, single, and visible as they accomplish the task. The therapist should encourage the patient to keep the eyes working together and keep the targets clear throughout each activity.

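### The SAP aims to show efficacy and programme impact from before-after change in one team with no described control, and states no limit on attribution

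*SAP*

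**What the plan says.** The SAP is one paragraph. It names its design and purpose together: "This is a within-subject before-after design to assess the efficacy of sports vision training on functional visual skills". Near its end it defines how the programme will be judged: "We will evaluate the impact of the sports vision program by comparing baseline values to final values for each primary outcome measure". The analysis is given as "Parametric repeated measures ANOVA will be used with post-hoc t-tests corrected for multiple comparisons".

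Two main outcomes are listed. The first is a Senaptec Sensory re-evaluation against baseline, with percentiles from a Division 1 softball database. The second is "a comparison of baseline training performance to post training performance in sports vision training activities, such as Dynavision and Senaptec Sensory Trainer activities". A t-test is assigned to the second, introduced by the words "To analyze change in training performance". The SAP also intends to "adjust the significance level, to account for multiple tests being performed", but gives neither a method nor a number of tests.

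On who is studied, the opening of the Protocol says "There are 23 ladies on the softball team" and "The training will be a required once per week 45 minute training session". It sets an eight-week programme and places evaluations before and after training, a wash-out and a last evaluation outside those weeks. Task order changes weekly to deal with order effects. Neither document describes an untrained, sham or waiting-list group, or a second baseline measurement.

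**The concern.** Efficacy and impact are causal words. They claim that the programme produced the change, which requires some idea of what the same athletes would have scored without it. Nothing described in the documents supplies that. Athletes who take the Senaptec evaluation again may score better because they know the test, and a team's ordinary practice and season run alongside the eight weeks. Either could move the scores with no contribution from the programme.

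The conclusion is what is at stake. If the aim and impact sentences are followed as written, a significant change in the Senaptec re-evaluation will be reported as the effect of the programme, whatever its source.

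**Working it through.** **What the plan offers against this.** The SAP gives no sample-size calculation, effect size, SD or numerical alpha, so there is no figure of its own to reproduce. The question is whether any planned feature separates a programme effect from other change over time.

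- *Division 1 percentiles.* These place each athlete in a reference distribution. They are not described as repeated measurements of untrained athletes over the same interval.
- *Rotation of task order.* This deals with order effects among session tasks, not with growing familiarity.
- *Multiplicity correction.* This limits chance findings. A systematic shift in the mean is not a chance finding.
- *Wash-out and last evaluation.* A fall after the wash-out would fit simple retest familiarity less well, while a retained gain would be ambiguous. The SAP does not say which occasions enter the ANOVA and does not specify a contrast between the post evaluation and the evaluation after wash-out.

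**Illustration for the first outcome.** Suppose the programme has no effect and scores rise through retesting alone.

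Inputs: n = 23 (the roster; the documents do not give the number analysed). Assumed: retest gain g = 0.2, 0.3 or 0.5 SD; pre-post correlation r = 0.5 or 0.7; two-sided tests at 0.05, 0.025 (Bonferroni for 2) and 0.005 (Bonferroni for 10).

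Standardised change: dz = g / √(2(1 − r)). For r = 0.5 the divisor is √1 = 1; for r = 0.7 it is √0.6 = 0.775. The paired t-test has 22 degrees of freedom and noncentrality dz × √23, which runs from 0.2 × 4.796 = 0.96 to (0.5 / 0.775) × 4.796 = 3.10. Counting both tails, the probability of a significant result is:

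| g (SD) | r | 0.05 | 0.025 | 0.005 |
|---|---|---|---|---|
| 0.2 | 0.5 | 0.151 | 0.092 | 0.027 |
| 0.2 | 0.7 | 0.220 | 0.142 | 0.047 |
| 0.3 | 0.5 | 0.280 | 0.189 | 0.068 |
| 0.3 | 0.7 | 0.427 | 0.312 | 0.133 |
| 0.5 | 0.5 | 0.630 | 0.508 | 0.268 |
| 0.5 | 0.7 | 0.841 | 0.750 | 0.505 |

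The ranges are 15–84%, 9–75% and 3–51%. Correction lowers the rate, but the shift remains.

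**Repeated-measures ANOVA.** With two occasions it equals the paired t-test. With three occasions, means (0, g, g) and compound symmetry, λ = 23 × (2/3)g² / (1 − r) on 2 and 44 degrees of freedom. At 0.05 the result is 0.146 (g = 0.2, r = 0.5) to 0.881 (g = 0.5, r = 0.7), so 15–88%. The choice of test does not change the picture.

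**Smallest observed change that is significant.** tcrit / √23 × √(2(1 − r)). At 0.05, 2.074 / 4.796 = 0.432 SD for r = 0.5, and × 0.775 = 0.335 SD for r = 0.7. At 0.005, 3.119 / 4.796 = 0.650 SD and 0.504 SD. A change of that size reaches significance whatever caused it.

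**What a comparator would do.** In 20,000 simulated studies with a drift of 0.5 SD of the change score and no programme effect, the before-after test was significant in 63%. Comparing a hypothetical 12/11 split with the same drift in both groups was significant in 5%.

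**The second outcome.** The Protocol's task descriptions give two runs of each Dynavision setting per session, and three each of Near Far Shift and Spatial Memory. Over eight sessions that is 2 × 8 = 16 and 3 × 8 = 24. These are planned maxima, since staff may simply note a task that ran out of time.

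**The case against.** The strongest reply is that nothing is hidden. The SAP names a before-after design in its first sentence, no reader would mistake it for a controlled trial, and a limitation of this kind could go in the report. Single-team studies are legitimate. That stands as a reason not to ask for a different design. It does not answer the point, because the sentence that names the design also gives efficacy as its purpose, and no later sentence limits the inference.

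Four stronger readings are tempting, and the documents do not support them.

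- A reader might infer that the SAP uses gains on drilled tasks as evidence about functional visual skills. It never says so. It calls the second outcome training performance, and a practice gain there is a true change in that outcome. It also does not say whether its main and primary outcomes are the same set. The impact sentence merely fails to set the second outcome apart, which justifies a clarification and no more.
- A reader might infer that no comparison across the wash-out is planned. The post-hoc t-tests could include one if all occasions enter the ANOVA. What is missing is a statement of the occasions and the contrast.
- A reader might conclude that change in this study can never bear on the programme. That is too absolute, because the pattern across the wash-out could be informative. The limit applies to change from baseline taken alone.
- A reader might take the percentages above as this study's error rate. The documents give no retest gain, SD, correlation or number of tests, so the percentages cannot be that.

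**Conclusion.** The point holds as one about inference. The SAP states a causal aim and judges it by baseline-to-final change in one team with required training and no described control group or repeated baseline. That change alone cannot distinguish the programme from retest familiarity or concurrent change, and no planned feature is specified in a way that would.

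This conclusion rests on the text and does not depend on the calculations. They show only that bias of this kind could plausibly produce significance at n = 23, and that the planned correction would make such results less frequent without removing the bias. Every input to them except the roster size is assumed.

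The study and its analyses remain usable. What needs to change before results are read is the claim attached to them.

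**What to change.** Replace the two causal phrases in the SAP with wording such as: *estimate within-athlete change from baseline to [the post evaluation, the final evaluation after wash-out, or both]; without a control group, change from baseline alone does not establish that the programme caused it*. The bracket must be filled in, because the current reference to final values does not settle which evaluation is meant.

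Optional clarification: state that the second outcome measures progress on practised tasks and is reported separately from any conclusion about functional visual skills.

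Both are text edits. They add no visits, athletes, staff or analyses, and both main outcomes stay. The cost is a more modest headline claim.
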